## 6. INTRODUCTION

### 6.1. Pompe Disease

Pompe disease (Online Mendelian Inheritance in Man #232300, also known as acid maltase deficiency or glycogen storage disease type II) is an autosomal recessive genetic disorder caused by mutations in the gene encoding human acid  $\alpha$ -glucosidase (*GAA*). These mutations may result in complete absence or partial loss of endogenous human acid  $\alpha$ -glucosidase (GAA) activity, which is responsible for the breakdown of lysosomal glycogen. The enzyme deficiency results in accumulation of intracellular glycogen leading to progressive disruption of cellular function, particularly in the heart, skeletal muscles, and diaphragm. The age at onset of clinical manifestations, rate of progression, and severity, including degree of organ and/or muscular (skeletal, respiratory, and cardiac) involvement, largely depends on the severity of the mutations and consequently on the residual enzyme activity (Hirschhorn and Reuser 2001; Raben, Plotz et al. 2002). Lower enzyme activity is generally associated with a more severe clinical course of the disease (Kishnani, Steiner et al. 2006).

Pompe disease may be categorized into 2 classes: infantile-onset Pompe disease (classic and nonclassic) and late-onset Pompe disease (LOPD) (Leslie and Bailey 2017).

Late-onset Pompe disease can present at any age greater than 12 months and does not present with clinically apparent cardiac involvement (Leslie and Bailey 2017). Late-onset Pompe disease is often referred to as juvenile-onset Pompe disease when occurring in the pediatric subpopulation of the LOPD category. Late-onset Pompe disease has a slower rate of progression compared with infantile-onset Pompe disease, with most patients experiencing progressive limb-girdle weakness and respiratory failure due to involvement of muscles in the proximal lower and upper limbs, paraspinal muscles, and diaphragm. Clinical manifestations include difficulty walking, climbing stairs, and progressive limitations of motor activities of daily living with progression to a need for ambulatory support followed by wheelchair dependence (Hirschhorn and Reuser 2001). Clinical manifestations of the disease are compounded by respiratory involvement, initially as sleep-disordered breathing and orthopnea (shortness of breath in supine position). The progressive nature of Pompe disease generally results in the use of invasive mechanically assisted ventilation. Biochemical abnormalities include increased level of serum creatine kinase (CK), a biomarker of muscle injury, and urinary hexose tetrasaccharide (Hex4), a biomarker of disease substrate. Life expectancy for patients with LOPD can range from early childhood to late adulthood, depending on the age of onset, rate of disease progression, the extent of respiratory muscle involvement, and the presence of co-morbidities (Hagemans, Janssens et al. 2004).

Enzyme replacement therapy (ERT) with recombinant human acid  $\alpha$ -glucosidase (rhGAA), alglucosidase alfa, became available for all patients in Europe and the US in 2006. While alglucosidase alfa provides initial benefit to many patients, the magnitude and duration of therapeutic response with continuing therapy vary among individual patients (van der Ploeg, Clemens et al. 2010; Schoser, Stewart et al. 2017). The current ERT, at best, may offer improvement in measures of muscle function, strength and respiratory function for a finite duration followed by slow decline in these parameters (Toscano and Schoser 2013; Wyatt, Henley et al. 2012).

The most serious tolerability issue with alglucosidase alfa is the occurrence of infusion-associated reactions (IARs), which, in some instances can include life-threatening anaphylaxis or other severe allergic responses (Lumizyme® Prescribing Information, August 2014; Myozyme® Summary of Product Characteristics, December 2018). Management of these events include dose reduction, reduced infusion rates and prolonged infusion times, and dose interruption or discontinuation. Premedication with antihistamines and steroids (prior to infusion) is also regularly used to prevent and reduce the occurrence and severity of IARs and hypersensitivities related to alglucosidase alfa infusion. Despite these measures, patients with Pompe disease may still experience IARs, and some cannot tolerate regular infusions of the currently approved ERT.

Co-administration of ATB200 (rhGAA, cipaglucosidase alfa) with AT2221 (miglustat; *N*-butyl-deoxynojirimycin) (cipaglucosidase alfa/miglustat) is designed to address the limitations of alglucosidase alfa relating to duration of effect and tolerability issues with regard to IARs. Cipaglucosidase alfa has been approved in combination with miglustat in the EU, Great Britain, and other countries around the world for treatment of adults with LOPD, and in the US for the treatment of adults with LOPD who are not improving on their current ERT.

## **6.2. Cipaglucosidase Alfa/Miglustat**

Cipaglucosidase alfa/miglustat is a novel first-in-class co-administered product approach for the treatment of adult and pediatric patients with LOPD. Cipaglucosidase alfa/miglustat is being developed for co-administration for which (1) cipaglucosidase alfa is the main active substance (enzyme) that is engineered for optimal targeting to lysosomes, the site of glycogen catabolism in affected tissues, and (2) miglustat is a co-administered enzyme stabilizer that stabilizes cipaglucosidase alfa from denaturation in systemic circulation, which enhances the delivery of the active component cipaglucosidase alfa to lysosomes.

### **6.2.1. Cipaglucosidase Alfa**

Cipaglucosidase alfa is a next-generation rhGAA enzyme. Cipaglucosidase alfa differs structurally from currently approved rhGAA (alglucosidase alfa) enzyme. Based on the published literature, cipaglucosidase alfa matches the sequence for human alpha glucosidase but has important differences on its post-translational glycan structures that enable more rapid cellular uptake and lysosomal targeting of the enzyme.

### **6.2.2. Miglustat**

Miglustat is an iminosugar that functions as an enzyme stabilizer of cipaglucosidase alfa. Because cipaglucosidase alfa is a recombinant lysosomal enzyme, it is most stable at lysosomal acidic pH and thus is susceptible to denaturation and enzyme inactivation at neutral blood pH when administered intravenously (IV). Miglustat binds to cipaglucosidase alfa and protects cipaglucosidase alfa from denaturation in blood. This interaction of miglustat with cipaglucosidase alfa results in stabilization of the cipaglucosidase alfa enzyme in the blood and enhancement of the pharmacokinetics of the cipaglucosidase alfa leading to a more efficient percentage of active enzyme being delivered to key disease-relevant tissue (ie, muscles).

Miglustat capsules contain the same active ingredient, *N*-butyl-deoxynojirimycin (miglustat), as that in Zavesca® (Actelion Pharmaceuticals US Inc.), which is approved for the treatment of

adults with type I Gaucher disease (in the US and EU) and for treatment of adult and pediatric patients with Niemann Pick-C disease (in EU and Japan). Miglustat is administered at a lesser frequency (1 dose every 2 weeks) in contrast to dosing with miglustat for Gaucher disease and Niemann Pick-C disease (3 times daily) (see Section 11.5 for dosing for this study).

## 6.3. Human Dosing Rationale

The doses and regimen selected for evaluation in this study, 20 mg/kg cipaglucosidase alfa + 260 mg miglustat for subjects weighing  $\geq 50$  kg or 195 mg miglustat for subjects weighing  $\geq 40$  kg to  $< 50$  kg every 2 weeks, is the same as that evaluated in Study ATB200-03, the study preceding this study. Dose selection was based on a body of evidence that includes in vitro data demonstrating the stabilizing effects of miglustat on the cipaglucosidase alfa enzyme, nonclinical pharmacokinetic (PK)/pharmacodynamic (PD) data from studies conducted in the murine gene encoding acid  $\alpha$ -glucosidase (mouse protein) (ie, *Gaa*) knockout (KO) model, and clinical PK/PD, efficacy, and safety data from Phase 1/2 Study ATB200-02.

### 6.3.1. Cipaglucosidase Alfa

Dose selection of cipaglucosidase alfa 20 mg/kg was based on providing a comparable total protein dose for cipaglucosidase alfa as that approved for alglucosidase alfa, as determined by spectrophotometric analysis (ultraviolet absorbance 280 nm, A280), which showed comparable specific activity (GAA enzyme activity/mg protein/hour). Despite similar specific activities, an equivalent dose of 20 mg/kg administered to *Gaa* KO mice showed a PK profile of cipaglucosidase alfa distinct from alglucosidase alfa, as indicated by lower exposures. These lower exposures were due to faster clearance of cipaglucosidase alfa from plasma, which resulted in more efficient targeting and delivery of cipaglucosidase alfa into the disease-relevant muscles. At 20 mg/kg cipaglucosidase alfa, glycogen reduction was most effective and significantly improved compared with 20 mg/kg alglucosidase alfa in *Gaa* KO mice and was thus chosen as the dose to be tested in patients with Pompe disease.

Cipaglucosidase alfa is the primary active agent with an enzymatic mechanism of action that specifically reduces intramuscular glycogen, the primary lysosomal storage material in LOPD. Cipaglucosidase alfa differs structurally from the currently approved rhGAA (alglucosidase alfa) based on both its amino acid sequence and post-translational glycan structures and phosphorylation. One of the key features that distinguishes cipaglucosidase alfa from alglucosidase alfa is that substantially more (~95%) of the initial cipaglucosidase alfa dose binds cation-independent mannose 6-phosphate receptor (CI-MPR) compared with only ~27% of alglucosidase alfa at equivalent enzyme concentrations. The substantially higher binding of cipaglucosidase alfa to the CI-MPR receptor is due to the greater bis-M6P content of cipaglucosidase alfa compared with alglucosidase alfa, which has 10 times higher affinity to bind to the receptor compared with M6P. As a result, a significantly greater amount of cipaglucosidase alfa is internalized into the disease-relevant muscles compared with alglucosidase alfa and therefore, the former is more potent. In vitro studies have demonstrated this by improved uptake of cipaglucosidase alfa into muscle cells as well as by substantially greater glycogen reduction in disease-relevant muscles of *Gaa* KO mice with 20 mg/kg cipaglucosidase alfa compared with 20 mg/kg alglucosidase alfa. In addition, in vivo studies have indicated that the co-administration of miglustat with cipaglucosidase alfa shows even greater trends in glycogen reduction compared with either cipaglucosidase alfa alone or

alglucosidase alfa. Therefore, a 20 mg/kg dose of cipaglucosidase alfa with miglustat is expected to provide improved uptake into muscle tissue than even higher doses at 40 mg/kg of alglucosidase alfa.

### **6.3.2. Miglustat**

Dose selection for miglustat 260 mg was based on in vitro stability studies showing that miglustat at 17  $\mu$ M preserves cipaglucosidase alfa catalytic activity in blood of neutral pH at 37°C. In *Gaa* KO mice, oral co-administration of a dose approximating 17  $\mu$ M concentration (10 mg/kg) administered 30 minutes before IV administration of 20 mg/kg cipaglucosidase alfa showed most effective glycogen reduction in skeletal muscles compared with either cipaglucosidase alfa alone or alglucosidase alfa. Notably, miglustat at a concentration of 17  $\mu$ M approximates the resultant plasma concentration after oral dosing of 260 mg miglustat in the ongoing clinical study, ATB200-02, being conducted in patients with LOPD. Importantly, 260 mg miglustat provided maximal duration of binding and stabilization in plasma for up to 18 hours, with minimal duration of inhibition for up to only 4 hours in tissues (Modeling and Simulations to Support Dosing of cipaglucosidase alfa and miglustat for a First-In-Human Study in Patients with Late-Onset Pompe Disease, AMIC-PCS-102, September 2015).

For patients who weigh  $\geq$  40 kg to  $<$  50 kg, miglustat dose modification is necessary. Patients in this body weight category will receive 195 mg miglustat (3  $\times$  65-mg capsules).

Exposure-matching modeling and simulations for body weights of  $\geq$  40 kg to  $<$  50 kg for the 195 mg dose were similar to body weights of 70 kg at the 260 mg dose (ATB200 and AT2221 Population Pharmacokinetic Simulations and Exposure Matching for Pediatric Subjects, February 2019). Patients who have a baseline body weight of  $<$  50 kg, but gain weight during the study and reach a weight of 55 kg, will have the dose of miglustat increased to 260 mg (4  $\times$  65-mg capsules). If their body weight subsequently decreases and returns to a level below 50 kg, then the miglustat dose would be reduced to 195 mg (3  $\times$  65-mg capsules).

Additional information is provided in the Investigator's Brochure.

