## **10. TREATMENT OF SUBJECTS**

Subjects will receive cipaglucosidase alfa/miglustat as follows: miglustat 260 mg (4 × 65-mg oral capsules) for subjects weighing  $\geq 50$  kg or miglustat 195 mg (3 × 65-mg oral capsules) for subjects weighing  $\geq 40$  kg to  $< 50$  kg, followed approximately 1 hour later by cipaglucosidase alfa 20 mg/kg (reconstituted lyophilized drug product, 105 mg/vial), administered over a 4-hour IV infusion. The cipaglucosidase alfa/miglustat combination regimen will be administered every 2 weeks. Subjects are required to fast at least 2 hours before and 2 hours after administration of miglustat.

Study drug will be administered every 2 weeks at the study site. After 3 months in the study without any moderate to severe IARs, subjects may be eligible for administration of study drug at their home (see Section 12.2.2). In countries or at sites where the administration of alglucosidase alfa is reserved for hospital use, however, all study drug will be administered in a hospital setting.

Cipaglucosidase alfa and miglustat will be administered under the supervision of study site personnel; therefore, treatment compliance will be calculated using study drug administration records.

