#### **11.5.2. Miglustat**

The dose of miglustat is 260 mg (4 × 65-mg oral capsules) for subjects weighing  $\geq 50$  kg and 195 mg (3 × 65-mg oral capsules) for subjects weighing  $\geq 40$  kg to  $< 50$  kg.

Miglustat is administered orally, approximately 1 hour before cipaglucosidase alfa infusion. Subjects will take 3 or 4 capsules of miglustat, depending on their body weight. Subjects should fast for at least 2 hours before and 2 hours after administration of miglustat. Fasting is defined as nothing by mouth except water; this includes prescription or over-the-counter medications, vitamins, or herbal supplements other than premedications for administration of cipaglucosidase alfa. If a medication is considered necessary for the health of the subject, approval must be obtained from the medical monitor unless in case of emergency. Therefore, subjects should arrive at the clinic at least 1 hour prior to the start of the cipaglucosidase alfa infusion to receive miglustat.

If a subject has received miglustat on a dosing day but then is unable to receive the infusion of cipaglucosidase alfa, the subject may be re-dosed with miglustat at least 24 hours later, prior to their rescheduled infusion of cipaglucosidase alfa.

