### **13.3.2. Overdose/Underdose**

A product overdose/underdose (whether accidental or intentional) is considered by Amicus to be an AE and must be recorded as such in EDC. If a subject experiences an overdose or an underdose during the course of the study (as defined below for each product, whether symptomatic or not), the Amicus medical monitor must be notified within 5 working days of the investigator or study personnel first becoming aware of the overdose/underdose.

- Overdose
  - cipaglucosidase alfa:  $\geq 20\%$  higher than the assigned dose of study drug for a single administration ( $20 \text{ mg/kg} \times \text{patient weight}$ )
  - miglustat:  $\geq 1$  capsule more than the assigned dose of study drug for a single administration

- Underdose
  - cipaglucosidase alfa:  $\geq 20\%$  lower than the assigned dose of study drug for a single administration ( $20 \text{ mg/kg} \times \text{patient weight}$ )
  - miglustat:  $\geq 1$  capsule less than the assigned dose of study drug for a single administration (eg, if a subject is supposed to receive 4 capsules, but only receives 1, 2, or 3 capsules; or if a subject is supposed to receive 3 capsules but only receives 1 or 2 capsules)

Follow-up information must be forwarded on the outcome of the overdose/underdose as applicable. If an SAE occurs in conjunction with the overdose/underdose, the same SAE reporting requirements described in Section 13.3 apply.

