### **5.3.1. Study Compliance**

Compliance will be provided separately for cipaglucosidase alfa and miglustat. For each subject taking cipaglucosidase alfa, compliance will be calculated based on the number of infusions as well as the actual infusion dose administered.

Compliance based on infusion dose is calculated as:

100\*(total infusion dose administered [mg] / total infusion dose planned or intended [mg]).

Compliance based on number of infusions is calculated as:

100\*(number of infusions administered / number of infusions planned or intended),

where the number of infusions planned is obtained as: (subject's last date in ATB200-07 as of the data cut-off date – date of first infusion + 14) / 14.

Compliance for each subject taking miglustat will be calculated as:

100\*(total dose administered [mg] / planned dose [mg]).

Dose compliance rate will be classified as under-compliance: < 80%, within compliance: (80%, 120%), and over-compliance: > 120%.

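### Protocol Section 6.3.2 and the dosing sections give miglustat doses one capsule apart for a subject who starts below 50 kg and rises to 50 to <55 kg, and nothing says which sets the assigned dose

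*Protocol*

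**What the plan says.** Protocol Section 6.3.2 first sets the lower weight category, 40 to <50 kg: "Patients in this body weight category will receive 195 mg miglustat". It then gives a rule for change during the study. Subjects whose baseline weight is below 50 kg and who "gain weight during the study and reach a weight of 55 kg, will have the dose of miglustat increased to 260 mg". In the other direction: "If their body weight subsequently decreases and returns to a level below 50 kg, then the miglustat dose would be reduced to 195 mg". The section does not state the dose between 50 and 55 kg on the way up. By implication it remains 195 mg.

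The operative dosing text has a single cut at 50 kg. Section 10 gives "miglustat 260 mg (4 × 65-mg oral capsules) for subjects weighing" 50 kg or more, and 195 mg for 40 to <50 kg. Section 11.5.2 does the same ("The dose of miglustat is 260 mg (4 × 65-mg oral capsules) for subjects weighing" 50 kg or more) and adds: "Subjects will take 3 or 4 capsules of miglustat, depending on their body weight". The synopsis, Section 6.3 and SAP Section 3.2 repeat the 50 kg cut. None of these five places mentions 55 kg or points to Section 6.3.2. Section 6.2.2 sends the reader to Section 11.5 for the dosing in this study.

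Two later rules depend on the assigned or planned dose. Section 13.3.2 defines a miglustat underdose as at least 1 "capsule less than the assigned dose of study drug for a single administration", and an overdose as the mirror image. Either is an adverse event to be recorded whether or not there are symptoms. SAP Section 5.3.1 divides total miglustat given by the planned dose, which it does not define, and states: "Dose compliance rate will be classified as under-compliance: < 80"%, with over-compliance above 120%.

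**The concern.** A site that reads only Sections 10 and 11.5.2 would give four capsules to a subject who has risen from 48 to 52 kg. A site that also applies Section 6.3.2 would give three. Both would be following the protocol.

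Safety is the primary objective, and Section 13.3.2 turns a one-capsule deviation into a recorded adverse event with notification of the medical monitor. Whether such an event exists for this subject would depend on which section the site, the dosing system and the monitor each took as the source of the assigned dose. The same uncertainty carries into the miglustat compliance summary, because the SAP programmer must choose a planned dose without a definition. Appendix 1 refers back to Sections 10 and 11 for treatment, so subjects continuing under Amendment 3 inherit the conflict.

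**Working it through.** **Inputs.** Capsule strength 65 mg. The 50 kg cut (synopsis; Protocol Sections 6.3, 10 and 11.5.2; SAP Section 3.2). Changes at 55 kg upward and below 50 kg downward (Section 6.3.2). Limit of at least 1 capsule from the assigned dose (Section 13.3.2). Compliance limits of 80% and 120% (SAP Section 5.3.1).

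**1. The plan's own doses.** 4 × 65 = 260 mg and 3 × 65 = 195 mg. Both reproduce.

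**2. The two rules along one weight path.** The illustrative subject starts at 48 kg, rises to 55 kg and falls back. The 50 kg cut is applied to current weight.

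| Weight (kg), in order | Section 6.3.2 | 50 kg cut | Difference |
|---|---|---|---|
| 48, 49.9 | 195 mg | 195 mg | 0 |
| 50, 52, 54.9 (rising) | 195 mg (implied) | 260 mg | 1 capsule |
| 55 | 260 mg | 260 mg | 0 |
| 54, 52, 50 (falling) | 260 mg | 260 mg | 0 |
| 49.9 | 195 mg | 195 mg | 0 |

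The rules differ only in the rising part of the band, before 55 kg is first reached.

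**3. Against Section 13.3.2.** Four capsules given where Section 6.3.2 assigns three is +1, an overdose. Three given where the 50 kg cut assigns four is −1, an underdose. A dose judged against the rule that assigned it differs by 0, so there is no event.

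**4. Compliance per dose in the band.** 195/260 = 75.0%, below 80%. 260/195 = 133.3%, above 120%. Each ratio sets the dose given under one rule against the dose planned under the other.

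**5. Compliance per subject.** SAP Section 5.3.1 uses totals. Let f be the share of a subject's doses in the band, with every other dose given as planned.

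- Under-compliance, other doses 260 mg: 1 − 0.25f < 0.80, so f > 0.20/0.25 = 80%.
- Under-compliance, other doses 195 mg: 195/(195 + 65f) < 0.80, so f > 39/52 = 75%.
- Over-compliance, other doses 195 mg: 1 + f/3 > 1.20, so f > 0.20 × 3 = 60%.
- Over-compliance, other doses 260 mg: 260/(260 − 65f) > 1.20, so f > 52/78 = 66.7%.

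The overall class therefore changes only above about 75–80% of doses in the band (under) or 60–67% (over), depending on the dose outside it.

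**The case against.** The best defence is that the sections can be read together. Section 6.3.2 speaks of baseline weight and uses different triggers up and down, so the 5 kg gap looks deliberate. If the 50 kg cut elsewhere is a starting rule based on baseline weight, Section 6.3.2 is its adjustment rule and there is no contradiction. The documents do not exclude this reading, but no text states it. Section 11.5.1 names the last weight in the interactive response system for cipaglucosidase alfa only. Section 12.3.5 says weight is entered to calculate dose without naming the drug. Even on this reading, Section 11.5.2, where the reader is sent for dosing, lacks the adjustment rule.

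It is also fair to say that the dosing-system algorithm and the pharmacy manual are not among the documents and may apply one rule consistently. That would limit the practical effect. It would not tell a reader of the protocol or SAP what the assigned dose is.

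Three stronger readings are tempting and are not supported:

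- A reader might infer that the dose breaches the overdose/underdose limit whichever section is followed. It does not. The limit is relative to the assigned dose, so a breach needs one section to assign and another to judge.
- A reader might take 75% or 133% as a subject's compliance result. These are per-dose figures; step 5 shows how much of a subject's treatment must lie in the band before the class changes.
- A reader might count up to 26 dosing-error events a year (52 weeks / 2). That needs a subject in the rising band all year, with every administration judged against the rule not used to assign it. Nothing in the documents makes this likely.

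**Conclusion.** The inconsistency is real and narrow. It concerns subjects with baseline weight below 50 kg who rise to 50 to <55 kg and have not yet reached 55 kg. For them Section 6.3.2 implies 195 mg and five other places give 260 mg. This rests on two assumptions: that the 50 kg cut refers to current weight, and that 195 mg continues until 55 kg, which Section 6.3.2 implies but does not write out.

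The gap is one capsule (65 mg), which equals the limit in Section 13.3.2. The same administration can be correct or a recordable adverse event depending on the section used. The effect on compliance classes is conditional and limited. The documents give no count of affected subjects. The maximum enrolment is about 110, and the number in this band is probably small. The point should be corrected because it leaves a dose instruction ambiguous and feeds adverse event recording, not because it is likely to shift the study's overall results. No view is taken on which dose or threshold is right.

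**What to change.** Reconcile Section 6.3.2 with the synopsis, Sections 6.3, 10 and 11.5.2 and SAP Section 3.2, so that one rule gives the miglustat dose when a subject's weight crosses 50 kg. State in Section 11.5.2 whether baseline or current weight decides, and which recorded weight is used. Name that same rule as the assigned dose in Section 13.3.2 and the planned dose in SAP Section 5.3.1. Check that the interactive response system applies it. Which rule is right is for the sponsor.

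The cost is wording in the protocol and SAP and one check of the system's dosing rule. No new data collection is needed.
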